8.7. Other Assessments

Other safety assessments include weight, pubertal status, fundoscopy and bone age.

Weight and pubertal status are measured at each visit. Summary tables will be produced for these assessments by visit.

Fundoscopy is measured during the end of study. A listing will be presented for fundoscopy at each visit.

Bone age and delay in bone age are measured annually. Summary of the change from baseline will be presented in tables. Listing will also be provided. for bone age and delay in bone age.

9. Efficacy Analyses

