During Visit 1 (and again on Day 1, if on a subsequent day), the investigator will review all baseline data collected to determine the subject's eligibility. Data collected up through the final visit of the prior trial may be used as baseline data for the extension trial. The following will be performed for Visit 1 of the extension trial:

1. Medications and health status review

- Medical history from the prior trial will be carried forward into this trial

-
- Ongoing AEs from the prior trial will be followed until resolution or stabilization
 - Review of subject diary from the prior trial
 - Current therapies
 - Interval history since last visit of prior trial
2. Vital sign measurements
 3. Height and weight measurements
 4. Physical examination
 - Local tolerability assessment. **For subjects who were treated with Genotropin in the prior TransCon hGH CT-301 trial**, Visit 1 injection site examinations to the daily hGH treatment areas should be explicitly documented so as to differentiate from any new reactions that occur during the extension trial.
 5. Pubertal status assessment (Tanner stage, including onset of menses)
 6. Blood collection for the following laboratory assessments*:
 - IGF-1 and IGFBP-3
 - Antibodies against hGH and PEG
 - These analyses may only be conducted after enrollment and are not required for eligibility verification. These data will be used to support evaluation of post-dose antibody detection
 - If warranted, TransCon hGH, hGH, and PEG serum levels may be analyzed for the interpretation of immunogenicity titers
 - mPEG
 - Hormone/glycemic status (TSH, FT4, FT3, morning cortisol, and HbA1c)
 - Chemistry
 - Hematology
 - Lipid panel
 - **Females of child-bearing potential only:** hCG
- *Fasting not required. Banked blood samples may be used for additional characterization of anti-drug antibody responses.
7. Bone age x-ray
 - A bone age x-ray performed within approximately the past 52 weeks may be acceptable with appropriate documentation. However, if the last recorded bone age was > 12.0 years, and the bone age x-ray was performed greater than 9 months prior to Visit 1, a bone age x-ray should be performed within approximately 4 weeks of Visit 1.

8. Investigational product preparation/administration training/re-training

- May also be performed at other visits, as needed
- Includes review of the TransCon hGH Instructions for Use (also provided to the subject/parent/legal guardian/caregiver for reference throughout the trial)

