- ³ Medications and health status: Interval history only to be recorded in case of new disease states since the last visit of the prior trial; disease states diagnosed since the initiation of the prior trial (eg, new onset migraines) are medical history; Medical history from the prior trial will be carried forward into this trial's database; Ongoing AEs from the prior trial will be followed until resolution or stabilization; Review of subject diary from the prior trial; Current therapies.
- ⁴ Vital sign measurements include heart rate, blood pressure, respiratory rate and body temperature, which should be performed after the subject has rested for at least 5 minutes.
- ⁵ Height should be measured at each visit at approximately the same time of day, preferably by the same auxologist.
- ⁶ Blood sample collection – A includes IGF-1, IGFBP-3, antibodies against hGH and PEG, and for females of child-bearing potential hCG. If warranted, TransCon hGH, hGH, and PEG serum levels may be analyzed for the interpretation of immunogenicity titers
- ⁷ Blood sample collection – B includes mPEG, hormone/glycemic status (TSH, FT4, FT3, morning cortisol, and HbA1c), chemistry, hematology, and lipid panel. Fasting not required.
- ⁸ Bone age x-ray may not be required at Visit 1 if there is documentation of a bone age x-ray performed within the past 52 weeks. However, if subject's prior documented bone age was > 12.0 years, and it was performed greater than 9 months prior to Visit 1, a bone age x-ray should be performed within approximately 4 weeks of Visit 1. Bone age x-ray may also be performed at any time, if clinically indicated.
- ⁹ Once the GH Auto-Injector is available, transition to the GH Auto-Injector will occur in the US (only) at the next regularly scheduled trial visit when thorough training on preparation and administration will occur.
- ¹⁰ At Visit 1, the C&OS-P, CSDS-P, and CSDS-C should be completed for all subjects.

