- 3 Interval history, medications and health status: disease states diagnosed since the initiation of the prior trial (eg, new onset migraines) are medical history; Medical history from the prior trial will be carried forward into this trial's database; Ongoing AEs from the prior trial will be followed until resolution or stabilization; Review of subject diary from the prior trial; Current therapies.
- 4 Vital sign measurements include heart rate, blood pressure, respiratory rate and body temperature, which should be performed after the subject has rested for at least 5 minutes.
- 5 Height should be measured at each visit at approximately the same time of day, preferably by the same auxologist.
- 6 Blood sample collection – A includes IGF-1, IGFBP-3, antibodies against hGH and PEG, and for females of child-bearing potential hCG. If warranted, TransCon hGH, hGH, and PEG serum levels may be analyzed for the interpretation of immunogenicity titers
- 7 Blood sample collection – B includes mPEG, hormone/glycemic status (TSH, FT4, FT3, morning cortisol, and HbA1c), chemistry, hematology, and lipid panel. Fasting not required.
- 8 Bone age x-ray may not be required at Visit 1 if there is documentation of a bone age x-ray performed within the past 52 weeks. However, if subject's prior documented bone age was > 12.0 years, and it was performed greater than 9 months prior to Visit 1, a bone age x-ray should be performed within approximately 4 weeks of Visit 1. Bone age x-ray may also be performed at any time, if clinically indicated.
- 9 Once the auto-injector is available, transition to the auto-injector will occur in select countries at the next regularly scheduled trial visit when thorough training on preparation and administration will occur.
- 10 At Visit 1, the C&OS-P, CSDS-P, and CSDS-C should be completed for all subjects.

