5.1. Baseline Data

Two baselines are defined. One is referred to as parent study baseline and the other one is extension study baseline.

Parent study baseline is defined as the last non-missing assessment collected before the first study treatment in the parent study. Extension study baseline is defined as the last non-missing assessment collected before the first study treatment in the extension study. Some of the information does not change and are only collected in parent studies, i.e., race, gender, and parent heights. In those cases, parent baseline data will be carried into extension study to serve as the baseline values.

For majority endpoints, including height, IGF-1 and etc., the extension study baseline values will be utilized for the analysis except for antibodies. For antibodies, the status before the first dose of TransCon will be considered as the baseline.

For annualized height, the rolling baseline will be used to calculate the annualized height velocity to make sure there is one-year gap in the calculation. In other words, from the 15-month (65 weeks) visit onwards, the baseline value used for each successive HV calculation was the patient's height at the visit 52 weeks previously, e.g. height at 13 week served as the baseline value to determine HV at the 65 week ('moving 52 weeks HV basis'). If height at visit 52 weeks previously is missing then most recent height prior to the visit will be used.

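### Bone-age change from the extension baseline has no interval term, so the change labelled Week 52 can cover nominally 52 to 104 weeks

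*SAP*

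**What the plan says.** SAP 8.7 places bone age among the other safety assessments and plans this: "Bone age and delay in bone age are measured annually. Summary of the change from baseline will be presented in tables". Four further provisions decide what that change measures.

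- **Age of the baseline film.** Protocol 10.2.1 says of Visit 1: "A bone age x-ray performed within approximately the past 52 weeks may be acceptable with appropriate documentation". The SAP's own Schedule of Events, note 8, agrees: "Bone age x-ray may not be required at Visit 1 if there is documentation of a bone age x-ray performed within the past 52 weeks". There is one exception. It applies "if the last recorded bone age was > 12.0 years" and the film was taken "greater than 9 months prior to Visit 1, a bone age x-ray should be performed within approximately 4 weeks of Visit 1".
- **Choice of baseline.** SAP 5.1: "Extension study baseline is defined as the last non-missing assessment collected before the first study treatment in the extension study". It adds: "For majority endpoints, including height, IGF-1 and etc., the extension study baseline values will be utilized for the analysis except for antibodies". SAP 7.1 lists bone age among the extension-baseline characteristics.
- **Definition of change.** SAP Table 3 subtracts the baseline value from the later value and does not divide by elapsed time.
- **Next film.** Protocol 10.2.2.6 schedules films annually, at Visit 5 (Week 52), Visit 9 and so on.

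Height velocity is treated differently. SAP Table 3 divides height gain by the actual days between visits, and from Week 65 a rolling baseline is meant to keep a one-year gap. Nothing comparable is written for bone age.

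**The concern.** Bone age advances with time, so a change in it means little without the interval it covers. Here the interval is 52 weeks plus the age of the baseline film, and that age may differ from child to child. A reader of a Week 52 column will take the figure as one year on the extension. If many baseline films are old, ordinary maturation in raw bone age will look faster than it was. The trial has no concurrent control, so no comparison group within the table would reveal this.

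The content of the interval matters too. CT-301 has its primary endpoint after 52 weeks of treatment (Protocol 5.3), so a film about 52 weeks old at Visit 1 dates from about the start of that trial. For a child from the Genotropin arm, the extension change would then contain up to about a year on daily hGH.

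**Working it through.** **1. The plan's own window.** SAP Table 2, general row with x = 5: target day 7 × 13 × 4 − 1 = 363; lower limit Floor(91 × 3.5) = 318; upper limit Floor(91 × 4.5) − 1 = 408. These match the printed Visit 5 row.

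**2. Interval covered.** Let a be the film's age in weeks at Visit 1, with no gap between Visit 1 and the first dose. The nominal interval is 52 + a, and its ratio to the labelled interval is (52 + a)/52. The documents give no rate of bone-age advance, so the last column assumes 0.8, 1.0 or 1.2 bone-age years per year.

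| a (weeks) | Interval (weeks) | Ratio | Tabulated change (years) at 0.8 / 1.0 / 1.2 |
|---|---|---|---|
| 0 | 52 | 1.00 | 0.8 / 1.0 / 1.2 |
| 26 | 78 | 1.50 | 1.2 / 1.5 / 1.8 |
| 39 | 91 | 1.75 | 1.4 / 1.75 / 2.1 |
| 52 | 104 | 2.00 | 1.6 / 2.0 / 2.4 |

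The 39-week row (about 9 months) is the nominal maximum at bone age above 12.0 years when the exception yields a film before dosing. The 26-week row fits a film from the start of the 6-month CT-302 trial.

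**3. Outer limit.** Protocol 10.2.1 allows about 6 weeks between the final prior-trial visit and the first dose, and exempts the film from repetition after a 4 to 6 week gap. With a 52-week-old film, a 6-week gap and the next film on day 408, the interval is 364 + 42 + 407 = 813 days, about 116 weeks.

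**4. Later visits.** At Visit 9 a 52-week-old film gives (104 + 52)/104 = 1.5, so the distortion shrinks but does not vanish.

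**5. Group means.** If a share p of baseline films were 52 weeks old and the rest current, the mean interval would be 52 + 52p weeks: 65 at p = 25%, 78 at 50%, 104 at 100%. The documents do not give p.

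**6. Delay in bone age.** SAP Table 3 does not define it. Take delay as chronological age minus bone age, film age f in years and advance r per year.

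- Chronological age at the film date: change in delay over the interval is (1 + f)(1 − r). With f = 1 this is 0.4, 0 and −0.4 years for r = 0.8, 1.0 and 1.2, against true one-year changes of 0.2, 0 and −0.2.
- Chronological age at Visit 1 with the old film: baseline delay is too large by f, so with f = 1 the changes become −0.6, −1.0 and −1.4 years.

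**The case against.** The strongest reply is that delay, reported beside bone age, already adjusts for elapsed time. With chronological age taken at the film date and an advance of one year per year, the change in delay is zero whatever the film's age. This stands for that rate: the artefact is then confined to raw bone age read as a one-year change. At any other rate, the change in delay is scaled by the same factor as bone age (step 6).

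Second, the size rests on facts outside these documents. The synopsis has Visit 1 procedures done unless they were done at the prior trial's final visit. If the parent trials took a film at that visit, film age is near zero and the problem disappears. This also stands. The documents permit old films but do not show how often they were used. A systematic difference between parent trials is likewise conjecture.

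Third, the table carries limited weight. Bone age is in neither list of safety endpoints (Protocol 14.1.1, SAP 3.3.1), and the summary is descriptive with no test attached. That limits the severity.

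A reader might also infer that children with bone age above 12.0 years keep the old film as baseline because the replacement comes after dosing. Note 8 of the protocol's Schedule of Events says only that "a bone age x-ray should be performed within approximately 4 weeks of Visit 1", without saying before or after. Because closed epiphyses are an exclusion and eligibility is reviewed at Visit 1 and again on Day 1, a film before dosing is the more natural reading. Nor is it established that a later film would be mapped to Week 13: SAP 5.3 maps visits by scheduled assessment, and bone age is not scheduled then.

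**Conclusion.** The point holds as an upper-limit statement. As written, the Week 52 change in bone age covers nominally 52 to 104 weeks, or at most about 91 weeks at bone age above 12.0 years when the 9-month rule yields a film before dosing. Raw change read as one year is overstated by up to a factor of 2. This rests on the extension baseline applying to bone age, which follows from SAP 5.1 and 7.1 although 8.7 does not name it. The effect on group means cannot be stated without the distribution of film ages.

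Two stronger readings are not supported. One is that the artefact changes who leaves the trial: completion depends on absolute bone age (above 14.0 years for females, above 16.0 for males; Protocol 9.6.2 and 10.1), not on change from baseline. The other is that the SAP plans to compute delay wrongly: it leaves delay undefined, and nothing says that age at Visit 1 will be paired with an older film.

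Severity is minor to moderate, and confidence is moderate.

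**What to change.** In SAP 8.7 and Table 3:

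1. Summarise maturation as (bone age at later film − bone age at baseline film) / (chronological age at later film − chronological age at baseline film), with both ages taken on the film dates. This can stand beside the plain change or replace it.
2. Define delay in bone age as chronological age on the film date minus bone age.
3. Report the interval between films with each summary, so that any plain change can be read correctly.

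The baseline rule in SAP 5.1 can stay. Allowing a film taken after the first dose to serve as baseline would contradict it and is not needed, because the ratio allows for whatever interval occurred. If film ages vary widely, a sensitivity summary limited to baseline films taken close to Visit 1 would show how much they matter and would limit the prior-trial time included for former Genotropin subjects, which the ratio alone does not remove.

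The cost is a few lines of SAP text and a short derivation, with no new films or visits. Film dates must be available in the analysis data. The protocol requires documentation of an accepted film but does not say that its date is entered in the eCRF, so this should be checked first.

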9.1. Annualized HV

Annualized height velocity is calculated based on the rules stated in Section 5.4. Summary tables and listings for HV absolute values at each timepoint by each group and overall will be generated.

9.2. ΔHSDS

Height Standard Deviation Score is derived based on the rules stated in Section 5.4. Summary tables for absolute values and change from baseline at each timepoint by each group and overall will be generated. The listings will also be presented.

9.3. IGF-1 SDS and IGFBP-3 SDS

A descriptive table including the frequency and percentages of subjects at each visit by each group and overall will be presented where:

- IGF-1 SDS < - 2.0
- $0 \leq \text{IGF-1 SDS} \leq 2.0$
- $-2.0 \leq \text{IGF-1 SDS} < 2.0$
- $-1.0 \leq \text{IGF-1 SDS} \leq 2.0$
- IGF-1 SDS > 2.0
- IGF-1 SDS > 3.0

The absolute values and change from baseline at each visit of the IGF-1, IGFBP-3, IGF-1 SDS and IGFBP-3 SDS will be presented with descriptive statistics. Listings will be generated for these outcomes.

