8. SUBJECT POPULATION

Up to approximately 300 (male and female) children with GHD, completing a prior phase 3 TransCon hGH trial, still taking investigational product, who have no evidence of closed epiphyses, and meet all other entry criteria, will be invited to participate in the extension trial.

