14.1.2. Efficacy Endpoints

The efficacy endpoints of long-term weekly TransCon hGH treatment include the following:

- Annualized HV
- Δ HSDS
- Proportion of subjects with IGF-1 SDS of 0 to +2.0. Additionally, cut points of -2.0 to +2.0 and -1.0 to +2.0 will be assessed.
- IGF-1 SDS

- IGFBP-3 SDS

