3.3.2. Efficacy Endpoints

The efficacy endpoints of long-term weekly TransCon hGH treatment include the following:

- Annualized HV
- Δ HSDS
- Proportion of subjects with IGF-1 SDS of 0 to +2.0. Additionally, cut points of -2.0 to +2.0 and -1.0 to +2.0 will be assessed.
- IGF-1 SDS
- IGFBP-3 SDS

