5.4. Derived and Computed Variables

Table 3 provides the rules for derived and computed variables which have been initially identified as important for the analysis of the safety or efficacy as appropriate. It is expected that additional variables will be required. The SAP will not be amended for additional variables that are not related to the primary target or key secondary target variables. Any additional derived or computed variables will be identified and documented in the SAS programs that create the analysis files.

The birth date for each subject is collected on the eCRF. To be consistent with all the other TransCon hGH studies, the 15th day of the reported month is used to calculate the age and related scores. In such case, all the height SDS for the subjects will be calculated using 15th as the birth day. The HSDS reported in the eCRF will not be used as it is based on the actual birth date reported by the subject. FMD K&L will utilize the published SAS macro to calculate the height SDS and no independent QC is required for published SAS macro.

Table 3. Parameter Definition

Parameter	Definition
Annualized Height Velocity at visit x (HV) cm/year	$((\text{Height (Visit } x) - \text{Height (Visit } 1)) * 365) / (\text{Date (Visit } x) - \text{Date (Visit } 1))$ 
From the 15-month (65 weeks) visit onwards, the baseline value used for each successive HV calculation was the patient's height at the visit 52 weeks previously, e.g. height at 13 week served as the baseline value to determine HV at the 65 week ('moving 52 weeks HV basis'). If height at visit 52 weeks previously is missing then most recent height prior to the visit will be used.

Height Deviation Standardized Score (HSDS)	Height SDS will be derived using CDC 2000 (United States of America). A standard SAS program is published at: https://www.cdc.gov/nccdphp/dnpao/growthcharts/resources/sas.htm
Change from baseline	The value of each variable at each post-baseline time point minus the baseline score.
Normalized serum IGF-1 SDS	Proportion of subjects with IGF-1 Standard Deviation Score (SDS) of 0 to +2.0. Also derive for -2.0 to +2.0, -1.0 to +2.0.
Parents' Height SDS	$((\text{Parents Height}/M)^L - 1) / (L \times S)$ 
Where M=median, S= generalized coefficient of variation, and L= power in the Box-Cox transformation, the M, S, L values are obtained from the CDC website; Percentile Data Files with LMS Values

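### SAP 9.3 leaves a value of exactly 2.0 out of the supplementary -2.0 to +2.0 IGF-1 SDS band, although both narrower bands include it

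*SAP*

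**What the plan says.** SAP 9.3 asks for counts and percentages of subjects at each visit, by group and overall, in six IGF-1 SDS categories. Three are in-range bands that end at 2.0:

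- the main band: "0 \leq \text{IGF-1 SDS} \leq 2.0"
- the intermediate band, lower limit minus 1.0: "1.0 \leq \text{IGF-1 SDS} \leq 2.0" (minus sign before the quoted words)
- the wide band, lower limit minus 2.0: "2.0 \leq \text{IGF-1 SDS} < 2.0" (minus sign before the quoted words)

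The other three are < -2.0, > 2.0 and > 3.0.

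Elsewhere the three bands are written in one common form. Protocol 14.1.2 gives the 0 to +2.0 proportion as an efficacy endpoint and adds that "cut points of -2.0 to +2.0 and -1.0 to +2.0 will be assessed". SAP 3.3.2 repeats this: "Additionally, cut points of -2.0 to +2.0 and -1.0 to +2.0 will be assessed". The definition of normalized IGF-1 SDS in SAP 5.4, Table 3, starts from 0 to +2.0 and continues: "Also derive for -2.0 to +2.0, -1.0 to +2.0". None of these places separates the wide band from the other two at its upper end.

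**The concern.** Bands named 0 to 2.0, -1.0 to 2.0 and -2.0 to 2.0 should be nested, so that each wider band holds at least as many subjects as the one inside it. With one strict inequality in the widest band, that is no longer guaranteed. A reader could meet a table in which fewer subjects lie within -2.0 to +2.0 than within -1.0 to +2.0. A subject at exactly 2.0 would also be neither in the wide band nor above it.

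SAP 5.4 and SAP 9.3 also give a programmer two readings of one derived variable. Protocol section 14 makes the final SAP the analysis of record where the two documents differ, so the protocol's wording would not settle the matter.

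**Working it through.** **1. Where selected values fall under SAP 9.3 as written**

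| IGF-1 SDS | 0 to 2.0 | -1.0 to 2.0 | -2.0 to 2.0 (as coded) | > 2.0 |
|---|---|---|---|---|
| -1.5 | no | no | yes | no |
| -0.5 | no | yes | yes | no |
| 1.9 | yes | yes | yes | no |
| 2.0 | yes | yes | **no** | **no** |
| 2.1 | no | no | no | yes |

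Only the value 2.0 behaves inconsistently.

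**2. A small example.** Take four subjects at 0.5, 1.0, 1.5 and 2.0. As coded, the 0 to 2.0 band holds 4, the -1.0 to 2.0 band holds 4, and the wide band holds 3. With ≤ in the wide band, all three hold 4.

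**3. When the order of the bands reverses**

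- Wide count minus the -1.0 to 2.0 count = (number in [-2.0, -1.0)) - (number at exactly 2.0).
- Wide count minus the 0 to 2.0 count = (number in [-2.0, 0)) - (number at exactly 2.0).

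The wide band shows the smaller count only when the second term exceeds the first.

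**4. How many values equal 2.0.** The documents give neither the stored precision of IGF-1 SDS nor its on-treatment distribution. Assume a normal distribution with mean m = 0.5, 1.0 or 1.5 and SD s = 1.0 or 1.3. The share recorded as 2.0 is

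Φ((2 + h - m)/s) - Φ((2 - h - m)/s), with h = 0.05 for one decimal and h = 0.005 for two.

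- Lowest at one decimal (m = 0.5, s = 1.0): Φ(1.55) - Φ(1.45) = 1.30%.
- Highest at one decimal (m = 1.5, s = 1.0): Φ(0.55) - Φ(0.45) = 3.52%.
- Two decimals: 0.13% to 0.35%.
- Unrounded storage: close to zero.

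**5. How likely a reversal is.** This was simulated with 10,000 replicates per setting under the same normal assumption. The sizes were n = 300 (protocol section 8: "Up to approximately 300 (male and female) children with GHD") and n = 50. The latter is about the size of the former Genotropin group if all roll over, since protocol 5.3 gives about 150 children randomized 2:1 in CT-301 and 150 × 1/3 = 50.

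Chance that the wide count is below the -1.0 to 2.0 count (each range runs over SD 1.0 and 1.3):

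| Mean | n = 300, one decimal | n = 300, two decimals | n = 50, one decimal | n = 50, two decimals |
|---|---|---|---|---|
| 0.5 | 0 to 0.001 | 0 | 0.02 to 0.06 | 0.001 to 0.004 |
| 1.0 | 0.04 to 0.61 | 0 to 0.005 | 0.17 to 0.42 | 0.01 to 0.04 |
| 1.5 | 0.65 to 0.997 | 0.003 to 0.23 | 0.44 to 0.76 | 0.05 to 0.12 |

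The chance that the wide count is below the 0 to 2.0 count was at most 0.06 at n = 300 and at most 0.21 in any setting tried (n = 50, mean 1.5, SD 1.0, one decimal).

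**The case against.** The defence has several sound points.

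- **The band is supplementary.** The secondary objective concerns 0 to +2.0, and SAP 9.3 codes that with both limits included. The safety cut, > 2.0, is coded the same way in SAP 8.3 and 9.3. No hypothesis test uses the wide band. A reader might infer that the trial's main IGF-1 proportion is understated; the documents do not support that.
- **The rows were never meant to add up.** A reader might infer that < -2.0, -2.0 to 2.0 and > 2.0 ought to total 100% and now fail to. But SAP 9.3 lists overlapping cuts, not a partition. SAP section 5 also makes the default percentage denominator all subjects in the cohort, so missing values at a visit could keep the rows below 100% whichever sign is used.
- **The size is not established.** Multiplying 1.30-3.52% by 300 gives about 4 to 11 subjects per visit, and a reader might take that as the expected error. It requires one-decimal storage and 300 evaluable subjects at the visit, and the documents establish neither. At two decimals the same sum gives about 0.4 to 1.
- **A reversal is possible, not certain.** It is likely only with coarse rounding and a mean well above zero.
- **The sign might be a conversion error.** The text was extracted from PDF, and < for ≤ is a plausible misreading. The corresponding lines for the two narrower bands kept ≤, however, so this is a reason to check the source file and not to set the point aside.

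These arguments limit the consequence. They do not remove the mismatch, for which neither document offers a reason.

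**Conclusion.** The point holds as a minor specification error. The wide-band inequality in SAP 9.3 conflicts with SAP 3.3.2, SAP 5.4 and protocol 14.1.2, and with the two narrower bands in its own list. That follows from the text alone. The understatement in this row equals the share of subjects at exactly 2.0, so it arises only when such a value occurs. The percentages above rest on an assumed normal distribution and an assumed recorded precision, and the effect is negligible if scores are stored unrounded. No conclusion about safety or the 0 to +2.0 objective depends on it.

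**What to change.** In SAP 9.3, code the wide category as -2.0 ≤ IGF-1 SDS ≤ 2.0, after checking the sign in the source file. The three bands are then nested by construction, and every non-missing value falls in exactly one of < -2.0, -2.0 to 2.0 and > 2.0. It would also help to state in SAP 5.4 whether bands are assigned from the unrounded score or the reported one. The cost is one character in the SAP, plus a sentence if the precision is added. Data collection, trial conduct and the other rows of the table are unchanged.
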